**C. APPROACH**

This research is designed to integrate and leverage our team’s expertise (**Table 1**), as detailed in the *Personnel Justification* section, *Multiple PI Plan*, and *Biosketches*.

**C.1. Design overview.** **Table 2** depicts the logic model of the proposed study, and demonstrates its scientific rigor. Healthy Families America home visitors (see *Intervention arms* below for their qualifications) will be randomized to deliver the HVP curriculum with or without COPE for 12 months (standard HVP duration). Mothers/infants will be recruited and enrolled on a rolling basis over 24 months (study months 6-30), and

matched to a home visitor based on race, ethnicity and language preferences. Assessment of mothers and infants will be conducted by *assessment workers* (who are blind to study assignment) at enrollment, and after receiving 6 and 12 months of services. \*\*

	[name]	[name]	HFA	[name]	[name]	[name]	[name]
Infants and early childhood obesity/nutrition	x		x	x	x		
Home visitation services			x				x
Family-based behavioral obesity interventions	x						
Underserved, racial/ethnic populations and culturally/linguistically tailored interventions			x	x	x		x
Multilevel interventions for behavior change	x	x					
Social network measurement and analysis		x					
Longitudinal modeling of multilevel data		x				x	
Cost analyses of childhood prevention efforts							x

The assessment of participants after they ceased to receive services for a given period of time (i.e., “true” follow-up) is impossible because of the ongoing nature of HVP services. We believe that asking home visitors to withhold the delivery of the COPE material to allow for a “no COPE” period would be unrealistic in terms of potential contamination, and also create an uncomfortable situation for families and HVP staff.

SITUATION: More than 40% low-income children enrolled in federally funded programs are overweight or obese by age 5. Obesity efforts have limited impact among underserved, low-income children, at risk for obesity.		
INPUTS	OUTPUTS	OUTCOMES

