**C.5. Measurements.** HVP *Assessment Workers* (registered nurses who can draw blood) who enroll families into standard HVP services, have been trained to screen and recruit eligible families for the proposed project. They will administer the assessments (English or Spanish; **Table 6**) in the families’ homes or at the HVP clinic (as needed) at baseline/enrollment, and after 6mo and 12mo of services. *Home visitors* will be trained to gather interim (objective) weight measurements for the purpose of generating more frequent data points, triangulated with the assessment workers’ measurements.

**Medical and family history.** A thorough family history and physical examination will be conducted at baseline. We will collect demographic data, including socioeconomic status (education, income, eligibility for SNAP).

**Infant growth & waist trajectories.** Weight will be measured on a digital scale (Tanita) accurate to the nearest 5g. Length will be measured to the nearest 0.1 cm using an infanto-meter using the standardized WHO approach,

Table 6. Assessment time points (month of intervention) and key measures							
	Baseline	3	6	9	12	15	18
COVARIATES							
Demographics, household composition, medical history, post-partum depression, activity readiness	X						
MOTHERS							
Weight/height, waist circumference	X	X	X	X	X	X	X
Blood and vitals	X						X
24h diet & activity recall	X		X				X
Feeding and food insecurity	X		X				X
Social support and networks	X		X				X
Home environment	X		X				X
INFANTS							
Weight/length, waist circumference	X	X	X	X	X	X	X
Blood (finger prick)	X						X
24h diet & activity recall (from mother)	X		X				X

including use of staff training modules. Weight and length will be used to calculate weight-for-length and weight-for-age z-scores (WHO Standards), as recommended by the CDC for children <24 mos. Infant growth rates will be examined as the change in WLZ from baseline to follow up (12mo) Waist circumference will be measured at the umbilicus (nearest 1-mm) using a non-stretch measuring tape.

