**Aim 1 (maternal/infant outcomes).** Change in weight-related outcomes over the 2-year implementation is the primary outcome comparison. We will use multilevel regression models adjusting for clustering effect of home visitors to compare differences in the main outcomes across time by intervention arm. Regression model can be treated as a special case of path model without mediators. These regression models will include all participants, who have at least 2 measurements, regardless of when the measurements are taken, increasing the follow-up of study participants and statistical power. Specific measures relevant to Aim 1 are maternal and children weight-related measures. These models will allow the evaluation of intervention effects on, for example, child growth trajectory and activity, and mother BMI, metabolic, and behavior outcomes. Investigation of the main effects of COPE on outcomes will be conducted at each follow-up. Baseline outcome measures will be treated as covariates to control for potential

baseline differences. Effects of COPE will be evaluated first at each follow-up assessment point. Longitudinal analyses with all follow-up points (6 and 12 months) will then be conducted to examine profiles across time to investigate the effects of program conditions on trends of outcome measures.

**Aim 2 (maternal transmission).** To estimate the mediational effects of maternal transmission, multilevel path models will be developed and evaluated per our hypotheses. The model specification will be guided by our conceptual model treating Intervention program as the distal variables along with demographic variables to affect mother's weight, diet and behavior as mediators, which in turn may influence infants' outcome. While the intervention program will be at the Level-2 unit, all other variables included in the multilevel path models will be Level-1 variables obtained from mothers and children. Using breastfeeding and maternal diet on infants' weight trajectories as an example, the mediation mechanism of maternal transmission can be expressed by the process: COPE → breastfeeding \* maternal diet → weight. The path model will allow the test of both the direct effect of COPE on infant weight trajectory and its indirect effect on through breastfeeding and maternal diet.

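### The primary comparison names no single outcome and spans two years with no month-24 visit, and the text (6 and 12 months) conflicts with Tables 6 and 7 (6 and 18 months) on the full assessments.

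*Combined protocol and SAP*

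**What the plan says.** **Primary comparison.** C.6, Aim 1: "Change in weight-related outcomes over the 2-year implementation is the primary outcome comparison". The measures are described only as weight-related ones in mothers and children. The same paragraph plans "Longitudinal analyses with all follow-up points (6 and 12 months") and adds: "Investigation of the main effects of COPE on outcomes will be conducted at each follow-up".

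**Schedule in the text.** Section A, C.1, the C.5 text and the C.6 general strategy all give enrollment, 6 and 12 months. C.5 has assessment workers administer the assessments "at baseline/enrollment, and after 6mo and 12mo of services".

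**Schedule in the tables.** Table 6 counts months of intervention and ends at 18. Weight, height or length, and waist are marked every three months. Diet and activity, feeding and food insecurity, social networks and home environment are marked at baseline, 6 and 18. Blood is marked at baseline and 18 for mothers and infants. Table 7 lists a 6-month and an 18-month assessment and no other.

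**Candidate outcomes.** C.5: "Infant growth rates will be examined as the change in WLZ from baseline to follow up (12mo"). The power paragraph of C.6 refers to infant weight velocity as the main outcome, powers the weight outcomes as a group, and sets two-sided .05 for every test.

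**Who measures.** C.1 gives the assessments to workers "who are blind to study assignment) at enrollment, and after receiving 6 and 12 months of services". C.5 adds that home visitors, who deliver the arms, "will be trained to gather interim (objective) weight measurements".

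**Blood.** The biomarker text in C.5 limits the draw to mothers at baseline. Aim 1 compares changes in metabolic markers.

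**The concern.** A confirmatory comparison needs one variable, one time point and a visit at which the variable is measured. This plan fixes none of the three consistently. An analyst could report month 12 or month 18, mother or infant, and WLZ, weight velocity, BMI or waist, and could cite some part of the document for each choice. With .05 for every test and no hierarchy, such a choice raises the chance of a false positive claim.

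The schedule conflict also affects data collection. Staff who follow Table 6 will collect no diet, feeding, network or home data at month 12, although the analysis plan uses that wave for Aims 1 and 3a. Visits that were not made cannot be recovered. If the biomarker text is followed instead of Table 6, change in blood markers cannot be estimated.

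**Working it through.** **1. The plan's own figure.** The only quantitative statement tied to the weight outcomes is the detectable Cohen's f of .17 to .20, with N = 200 and inflation factors of 1.4 and 1.8. I checked whether it shows which schedule was assumed.

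- Effective N: 200/1.4 = 143 and 200/1.8 = 111.
- Between-arm F test with m repeated measures: noncentrality = N·m·f² / (1 + (m − 1)ρ). The plan does not state power, m or ρ, so I assumed 80% power and tried several values of m and ρ.
- 3 waves, ρ = .3: f = .172 and .196.
- 7 waves, ρ = .5: f = .178 and .203.

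Three waves (the text) and seven (the weight rows of Table 6) both come close to .17 to .20. The power statement does not settle the schedule.

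**2. The time points side by side.**

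| Source | Follow-up |
|---|---|
| C.6 Aim 1, opening sentence | 2 years |
| Section A, C.1, C.5 text, C.6 general strategy, C.6 Aim 1 longitudinal model | 6 and 12 months |
| C.5, infant WLZ change | 12 months |
| Table 6, body measurements | every 3 months to 18 |
| Table 6, diet, feeding, networks, home | 6 and 18 months |
| Table 6, blood | 18 months |
| C.5 biomarker text, blood | none (mothers, baseline only) |
| Table 7 | 6 and 18 months |

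No row gives month 24. The stated horizon is 24 months and the last scheduled assessment is month 18.

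**3. Is the 18 in the tables a slip?** C.1 ends enrollment at study month 30. Table 7 marks the 6-month assessment at study month 36 and the 18-month assessment at 48.

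- 30 + 6 = 36, which matches.
- 30 + 18 = 48, which matches.
- 30 + 12 = 42, for which there is no assessment row.

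Table 7 thus means 18 months after enrollment, and it agrees with Table 6.

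**4. Infant age.** Infants enter at 6 months of age.

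- 12-month visit: 6 + 12 = 18 months old.
- 18-month visit: 6 + 18 = 24 months old.

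C.5 justifies the z-scores "as recommended by the CDC for children <24 mos". An 18-month primary time point falls at that limit.

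**5. Multiplicity (illustration).** Take five weight outcomes (infant WLZ, weight-for-age z-score and waist; mother BMI and waist) at two follow-ups, each tested at two-sided .05.

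- Independent tests: 1 − 0.95^10 = 0.401.
- Correlated tests: 400,000 simulated sets of ten normal statistics with |z| > 1.96. Correlation is r between outcomes of the same person, t over time, r·t between different outcomes of that person at different times, and .1 between mother and infant (times t across time). All of these are assumptions.

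| r = t | Ten tests | One outcome, two times |
|---|---|---|
| .5 | 0.343 | 0.091 |
| .6 | 0.319 | 0.088 |
| .7 | 0.288 | 0.083 |
| .8 | 0.250 | 0.077 |

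Naming the variable but leaving the time point open still gives about 8% to 9%.

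**The case against.** The best reply is that, for weight, the plan already points to month 12. Five places in the text say 6 and 12 months, the WLZ definition stops at 12, the retention section describes a 12-month study, and Table 6 does have a month-12 weight. On this reading the two-year phrase is a leftover. WLZ change and weight velocity may also be two loose names for infant growth. This has force, and it is why month 12 is the natural repair. It does not remove the defect: the sentence that defines the primary comparison says two years, both tables run to 18 months, and nothing chooses between mother and infant.

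Two years could be counted from the start of home visits (6 months before enrollment plus 18), or could mean infant age at month 18. No section says either, and Table 6 is headed in months of intervention.

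On blinding, C.5 says that home-visitor weights are interim and are checked against those of the assessment workers, and that assessment workers measure mothers' weight. The month-12 weight may well be blinded. The doubt arises only if Table 6 is followed, where month 12 looks like an interim weight. This is a request for clarification.

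On blood, the restriction concerns blood draws. Blood pressure and heart rate are also measured, so change in those could still be estimated. The blood conflict does not touch the weight comparison.

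The error rates depend on a set of outcomes and correlations that the plan does not give. They show scale only. Table 7 was read from a PDF, so its marks are less certain than its row labels.

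**Conclusion.** The concern holds and must be fixed. These parts rest on the document's text alone:

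- the primary horizon of 24 months has no assessment, and the last one scheduled is month 18;
- the narrative and Tables 6 and 7 disagree, 12 against 18 months, on the later full assessment;
- no single variable is primary, and tests at each follow-up at .05 have no hierarchy.

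The size of the error inflation is illustrative: about 25% to 34% for ten correlated tests, 40% at independence, and 8% to 9% for one outcome at two times. The loss of 12-month diet, feeding and network data follows if Table 6 governs; 6-month mediators would remain. The loss of change in blood markers follows if the biomarker text governs. An unblinded month-12 weight follows only if home visitors take it.

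**What to change.** Replace the opening sentence of C.6, Aim 1 with one outcome at one month that has a scheduled, blinded assessment. For example: *The primary outcome is the between-arm difference in change in infant WLZ from baseline to month 12, measured by blinded assessment workers and tested at two-sided .05. All other outcomes and time points are secondary.* Month 12 is where the WLZ definition, the analysis plan and the weight row of Table 6 already agree.

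If the sponsor prefers weight velocity or month 18, the plan should state that, change C.1, C.5 and C.6 to match and, for month 18, say how WLZ is scored at 24 months of age.

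Then:

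- give one schedule in Section A, C.1, C.5, C.6 and Tables 6 and 7, with diet, feeding, network and blood measures at the waves that are analysed;
- say who takes the primary weight;
- reconcile the sections on the length of COPE delivery (two years in Section A and C.6, 12 months in C.1 and C.2). Which of these is right is for the sponsor to state.

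The cost is mainly wording. The other weight outcomes lose primary status. If month 12 is kept, the questionnaires and any follow-up blood draw move from month 18 to month 12. That may need an assessment-worker visit, and an office visit for blood, where Table 6 now shows only body measurements.

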*The proposed study builds upon the momentum, resources, and research infrastructure of our pilot work to test the larger-scale and sustained impact of COPE on infant's and mothers' obesity outcomes, and to study key mechanisms of maternal and social transmission on infants' obesity risk.* Specifically, 300 low-income mothers/infants enrolled in Healthy Families America HVP will be recruited and enrolled in the study, for an effective final sample of 200 mothers/infants. Based on standard HVP procedures, mothers/infants will be matched to highly trained home visitors (nurses) based on their ethnicity/race and language preferences. Home visitors, in turn, will be randomly assigned to deliver the standard HVP curriculum only or the standard HVP curriculum + COPE as part of their weekly home visits for two years of HVP services. Comprehensive assessments of mothers/infants will be conducted at enrollment and after 6 and 12 months of intervention.

**Specific Aim 1 (maternal and infant outcomes).** Test the direct effects of COPE on infants and mothers' weight, metabolic risks, diet/energy intake, and physical activity. This will be accomplished by comparing changes in body weight, metabolic markers, and eating and activity-related behaviors between infants/mothers across study arms (HVP only vs. HVP+COPE). These results will indicate whether HVP is an effective infrastructure for primary and secondary obesity prevention.

**Specific Aim 2 (maternal transmission).** Test whether breastfeeding and maternal diet and activity, feeding practices, and food insecurity mediate the effect of COPE on infants' outcomes. This aim will test mechanisms of maternal transmission on infants' obesity risks.

**Specific Aim 3 (social transmission).** **Aim 3** is two-pronged. **Aim 3a** tests the direct effect of HVP+COPE (vs. HVP only) on the characteristics of the social and community networks that surround mothers and infants (i.e., the density, composition, and quality of "health support networks"). **Aim 3b** tests whether the characteristics of social networks mediate the effects of COPE on maternal and infant outcomes. These findings will indicate if HVP obesity prevention efforts can alter and/or activate social network mechanisms.

**Secondary Aim.** Conduct a real-life economic analysis (costs, cost-savings, and non-monetary benefits) of integrating COPE into existing HVPs.

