**Power Analysis Aims 1-3 (Figure 7).** A total of 30 home visitors will be recruited and randomized to HVP or HVP+COPE. With an average of 13 families served by each visitor, a total of 300 families will be invited to participate in the proposed study over 12 months. Based on our pilot work and existing HVP data, we expect a retention rate of 75% of families, which will result in a final sample of 200 mothers/infants. We have calculated power using G\*Power based on an effective sample of N=200 for the main weight related outcomes with the design of repeated measurement. All tests use a two-sided alpha level of .05. Our pilot study showed a small to medium effect size of .4 (Cohen's *d*) on our main outcome of children's weight velocity and smaller effect on energy intake at 6 months post-test. No previous study has investigated the long-term (12 months) delivery of in-home obesity prevention on 0-2yo children's growth trajectory, diet and activity. However, an in-home intervention compared to outpatient pediatric counseling resulted in a large effect size of 1.64 (Cohen's *d*) for changes in zBMI at 12 months, among obese 2-5yo children. To account for potential large clustering effect at the home visitor level, we assume the intraclass correlation (ICC) of .05 to .1 with inflation factors  $(1+(n-1)*ICC)$  of 1.4 to 1.8, respectively. After taking inflation factor into account, our proposed sample size of 200 will have enough power to detect medium effect sizes based on Cohen's *f* between .17 and .20. More comprehensive path model will be specified in each aim for model evaluation and hypothesis testing. We are aware of the sample size limitation and will be cautious in the number of variables and the size of the model involved. We used the hypothesis-testing framework of RMSEA to estimate power of model fitting in our study. With  $\alpha = .05$ , a null hypothesis RMSEA of .00 (almost exact fit for path model), an alternative hypothesis RMSEA of .08 (criterion of not acceptable models) and degrees of freedom (size of the model) ranging from 10 to 15, the range of statistical power for a sample size of 300 is between .83 and .93. We will have sufficient power to detect small to medium effect of a set of pre-selected parameters associated with mediators and outcomes with sample size of 200.

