## PROTECTION OF HUMAN SUBJECTS

### A. Participants

This comparative effectiveness research involves the enrollment of 300 mothers/infants for a final effective sample of 200 mothers and their infants (age 6mo at enrollment).

**Inclusion of women.** Women are represented by mothers and female infants, which will be about half of the infant sample. Based on our projected effective sample of 200 mothers and their 200 infants (N=400), we anticipate that 75% of our sample will be women (100 children + 200 mothers = 300).

**Inclusion of racially and ethnically diverse families.** The families enrolled in the Home Visiting Program (HVP) from which the sample is drawn is culturally, racially and ethnically diverse, reflecting the population of low-income families enrolled in home visiting services in the Antelope Valley, CA area. Based on our HVP partner (Healthy Families America site in Southern California: Antelope Valley Partners for Health and Children's Bureau) clients' demographics and on our pilot work, we anticipate the following ethnic and racial distribution: 70% Hispanic/ Latino, 13% African American, 8% White, 5% American Indian/Alaskan, and 4% mixed/other race.

It is important to note that Health Families America (HFA) home visitors are matched to families based on language and cultural background. Home visitors are rigorously trained to understand, acknowledge, and respect families' cultural differences. Home visitors are selected because of their personal characteristics (i.e. non-judgmental, compassionate, ability to establish a trusting relationship, etc.), their experience working with culturally diverse communities, and their skills to do the job.

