### C. Recruitment and Retention

**Participant recruitment.** Low-income mothers and their infants (N=300, for a final effective sample of 200) will be participants in the study. Active participants will be low-income mothers and their infants (6mo-old at enrollment) drawn from mothers who are enrolled in HVP services at the Healthy Families America site/chapter in Antelope Valley, CA. Home visitors providing the HVP services will introduce the study to mothers, and study Assessment Workers will obtain written consent. Home visitors will clarify with mothers that their refusal to participate in the study is not affecting the services they provide. In our experience from our pilot research, families feel comfortable to refuse if they do not wish to participate. Of note, 90% of families receiving *Healthy Families America* HVP services choose to enroll in enhancement studies when offered (i.e., when a module is added to the core curriculum and evaluated). These rates are consistent with our pilot work.

**Inclusion/exclusion criteria.** Participants will be ineligible if either parent and/or child have a Dx of eating disorders (e.g., Anorexia Nervosa), Schizophrenia or Obesity-related syndrome (e.g., Prader Willi). Participants enrolled in a weight-loss program will be ineligible.

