**Retention.** Using conservative estimates, we anticipate that 25% of mothers enrolled will drop out of home visiting services over the 12-month study. Consequently, we will oversample at enrollment (N=300) to ensure an effective sample of 200 mothers and infants. We have learned a great deal about retaining mothers through our prior pilot studies. We attribute retention in part to our persistent efforts and abilities of the HVP home visitors, but also believe that there are unique features of home visited mothers that facilitate retention in a research study. For example, many of these mothers are socially isolated, and opportunities to exchange with their home visitor can be highly rewarding for mothers. We will use multiple strategies to retain the sample over the 12months of the implementation and assessments. We will rely on approaches widely used in studies of high-risk populations: (1) a gift card in the amount of \$25 at each data collection, with all incentives paid after each assessment/data collection *regardless of whether they complete the study*; (2) frequent contact with participants to maintain engagement because we believe that open communication between the team and participants is critical; (3) quarterly newsletters to update participants about study activities; (4) acknowledging birthdays; (5) participants are given a reminder phone call the day before the weekly visits and assessment sessions (or on Fridays for Monday assessment sessions).

**Informed consent procedure.** Informed consent, approved by the appropriate IRB, will be obtained by Antelope Valley Partners for Health assessment workers who are trained by our research team. All mothers that are enrolled in HFA's HVP services by Antelope Valley Partners for Health and Children's Bureau will receive a detailed explanation of the protocol, including any potential benefits and risks (in English or Spanish). Mothers will be required to sign the consent form (in Spanish or English) and provide consent for their infants. Only participants from whom consent is obtained will be involved in the study. Signed consents will be kept in the participants' files in locked filing cabinets. Each participant will receive a copy.

**Waiver.** No waiver or modification of consent is being requested from the IRB.

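### The power paragraph in C.6 prints 200 retained where 75% of 300 is 225, and labels as N=300 a model-fit power range that belongs to about N=270

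*Combined protocol and SAP*

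**What the plan says.** The power paragraph in C.6 sets 30 home visitors and then says: "With an average of 13 families served by each visitor, a total of 300 families will be invited to participate in the proposed study". It continues: "we expect a retention rate of 75% of families, which will result in a final sample of 200 mothers/infants". For clustering it assumes an ICC of .05 to .1 and, using 1+(n−1)×ICC, gives inflation factors "of 1.4 to 1.8, respectively", without stating n. It reports detectable Cohen's f of .17 to .20 at N=200 for the repeated-measures design. For the path models it takes alpha .05, null RMSEA .00, alternative RMSEA .08 and 10 to 15 degrees of freedom, and concludes that "the range of statistical power for a sample size of 300 is between .83 and .93".

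Elsewhere the 300 is not a number invited:
- A. Specific Aims: 300 mothers/infants "will be recruited and enrolled in the study, for an effective final sample of 200 mothers/infants".
- Protection of Human Subjects, A. Participants: the research "involves the enrollment of 300 mothers/infants for a final effective sample of 200 mothers and their infants".
- C. Recruitment and Retention, participant recruitment: 300 participants for a final 200. The same paragraph says that 90% of families receiving these "HVP services choose to enroll in enhancement studies when offered".
- C. Recruitment and Retention, retention: "we anticipate that 25% of mothers enrolled will drop out of home visiting services over the 12-month study". It then gives an oversample of 300 at enrolment as the consequence, to secure 200.

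**The concern.** The plan has one loss rate, 25%, and two sample sizes, 300 and 200, which that rate does not connect. C.6 presents 200 as the result of applying the rate, and the retention section takes the loss from mothers enrolled. Separately, the model-fit power is a fully specified calculation, so anyone can rerun it at the N it names, and it does not come out.

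Two things are at stake. Anyone monitoring recruitment needs to know whether 300 counts families approached or families enrolled, and what number is expected at the end. Aims 2 and 3 rest on path models, and the RMSEA range is the only numerical power given specifically for those models. It is tied to the wrong N, and the next sentence claims sufficient power for mediator and outcome parameters at 200.

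**Working it through.** **1. Retention.** Inputs: 300 families and 75% retention (C.6), or 25% dropout among those enrolled (C. Recruitment and Retention).

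- 300 × 0.75 = 225, against 200 printed.
- 200 / 300 = 0.667, so the printed pair implies 33% loss, not 25%.
- 200 / 0.75 = 267 would have to enrol to leave 200.

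**2. RMSEA power.** Inputs, all from C.6: alpha .05, null .00, alternative .08, df 10 and 15. Power = P[noncentral χ²(df, λ) > 95th percentile of central χ²(df)], with λ = (N−1) × df × 0.08².

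At N=300 and df 10, λ = 299 × 10 × 0.0064 = 19.136. The critical value is 18.307 and power is .8735.

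| N | df 10 | df 15 |
|---|---|---|
| 300 (as labelled) | .8735 | .957 |
| 270 | .828 | .930 |
| 225 | .736 | .863 |
| 200 | .672 | .808 |
| Printed, for 300 | .83 | .93 |

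Both printed values round correctly only for N=269 to 274. Using N in place of N−1 in λ moves that window to 268 to 273. Other conventions at N=300 do not rescue the label: alpha .025 gives .807 and .925, alpha .01 gives .706 and .868, and a close-fit null of .05 gives .413 and .533.

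**3. Inflation factors.** Solving 1+(n−1)×ICC for n:

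- ICC .05: (1.4−1)/.05 + 1 = 9.
- ICC .10: (1.8−1)/.10 + 1 = 9.

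Because the factors are printed to one decimal, n could lie between 8.5 and 9.5, which is about 255 to 285 families over 30 visitors. The cluster sizes a reader can derive from the text give:

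| Families per visitor | ICC .05 | ICC .10 |
|---|---|---|
| 13 (families served) | 1.60 | 2.20 |
| 10 (300/30) | 1.45 | 1.90 |
| 9 (implied) | 1.40 | 1.80 |
| 7.5 (225/30) | 1.33 | 1.65 |
| 6.67 (200/30) | 1.28 | 1.57 |

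**4. A flow that would fit.** 300 invited × 90% uptake = 270; 270/30 = 9 per visitor; 270 × 0.75 = 202.5, or about 200. This would explain the final sample, the inflation factors and the RMSEA range together. But no passage gives 270 as a sample size, and C.6 contains no uptake step, so it is an inference.

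**5. Cohen's f.** The target power and within-family correlation are not given in the text. Assuming 80% power, three waves and a correlation of .3, N=200 with factors 1.4 and 1.8 gives f = .172 and .196, in line with the printed .17 to .20. Other assumptions at other N also come close: N=270, two measures and a correlation of .5 give .176 and .199. So this range neither identifies N nor shows an error.

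**The case against.** The strongest reply is that nothing here hurts the trial. If 300 enrol and 25% leave, 225 exceeds the 200 used for the main power calculation, and 9 families per visitor inflates more than 6.67 or 7.5 would. That stands. A reader might infer from the mismatched figures that the study is underpowered for its weight outcomes; the documents do not support that.

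Second, 200 may be a planning floor. The retention section calls its estimates conservative, its 25% is dropout from services only, and mothers who become pregnant also leave the study (D. Protection Against Risk). This partly stands: 225 is an upper figure if other losses occur. But no other loss rate is given, no passage calls 200 a floor, and C.6 presents it as what 75% retention produces.

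Third, a reader might conclude that the true enrolment target is 270. Specific Aims, A. Participants and both paragraphs of C. Recruitment and Retention say 300, and only C.6 says invited. The back-calculation explains the numbers but does not establish an intention.

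Fourth, the lower model-fit power at 200 applies only if the path models use completers. C.6 plans intention-to-treat analysis with multiple imputation and/or full-information maximum likelihood, so families with partial data may contribute. It is also power to reject a poorly fitting model, not power for the COPE effect. Both points stand and limit what the lower figures mean. Neither makes .83 to .93 correct for N=300.

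**Conclusion.** Two stated figures in C.6 are wrong as written.

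- **Final sample:** it should be 225, not 200, if 25% is the loss from 300; alternatively, the loss is 33%.
- **Model-fit power:** for N=300 it is .87 to .96. The printed .83 to .93 belongs to about N=270. This uses the paragraph's own inputs and the standard noncentral chi-square calculation.

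Two related gaps go with them: the cluster size behind the inflation factors is unstated and matches neither 10 nor 13 per visitor, and the 300 is invited in one section and enrolled or participating in the others.

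The error in the RMSEA label runs against the plan at 300 (the true power is higher). At the retained N, if that is the N that applies, power is .74 to .86 (225) or .67 to .81 (200); at 200 it is below .80 for df 10 to 14. The f range of .17 to .20 is not in question. This should be fixed because the recruitment target and the power for Aims 2 and 3 are read from these figures.

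**What to change.** Make Specific Aims, C.6, A. Participants and both paragraphs of C. Recruitment and Retention give one flow, with invited, enrolled and retained numbers stated separately.

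- The plain repair is 300 enrolled and about 225 retained at 25% dropout. Alternatively, keep 200 as a declared planning floor and state the total loss of 33%, made up of dropout plus removals for pregnancy.
- If the sponsor did mean 300 invited and about 270 enrolled, all of those places must say so, including the participant-recruitment paragraph.
- State the families per visitor behind 1.4 to 1.8. Nine is conservative for the retained sample and may be kept.
- Correct the RMSEA sentence: print .87 to .96 for N=300, or relabel .83 to .93 as N=270. Add the power at the retained N (.74 to .86 at 225, .67 to .81 at 200), and say which N applies given the planned missing-data method.

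The cost is one rewritten paragraph and aligned wording elsewhere. No extra families and no change of analysis are needed. The price is that model-fit power at the retained N reads less favourably and, if the 270 flow is adopted, the stated enrolment falls from 300.
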